8.2.4.1. Enrollment

Patients must be consented before any data are collected. At the time of consent, the patient will be enrolled into the study. Participating study sites are required to enroll eligible patients consecutively into this study. If an eligible patient was approached and does not participate in the study, the reason for nonparticipation will be documented in the enrollment log.

Physicians who are routinely involved in the care and treatment of patients with MS will be targeted for recruitment. Efforts will be made to recruit a variety of Prescribing Physicians who are representative of Plegridy prescribers. Site selection criteria will include the projected availability of eligible patients in a 12 month enrollment period and the availability of time for the physician (and other site staff) to complete the electronic case report forms (eCRFs). To the extent possible, representative sites reflective of the treatment patterns within each country will be recruited. Selection criteria and basic site information (e.g., site size, investigator specialty, site type) will be collected via a site qualification questionnaire.

Patients with MS who are newly or currently prescribed Plegridy under routine clinical practice, and according to the local label, or who were previously participating in Study 105MS302 or Study 105MS303 are eligible to participate in this study and will be enrolled at the time of presentation of a routine clinic visit. No clinic visits are required as part of participation in this study. All clinical assessments are intended to be performed at the time of a routine clinical encounter or by referencing the medical record. PROs will be completed by patients either electronically or on paper. Electronic PROs can be accessed via a secure, personalized link either at the time of a routine clinic visit or outside of the clinic within four weeks of the visit. PROs can be completed on paper at the time of a routine clinic visit and responses will be subject to electronic data capture (EDC) by the site. If patients do not complete the PROs during their routine clinic visit, they can complete the PROs electronically through the secure, personalized link within four weeks of their routine clinic visit.

CONFIDENTIAL

The information contained herein may not be used, disclosed, or published without the written consent of Biogen MA Inc.

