Eligible patients may be naïve to Plegridy at the time of enrollment, but need not be naïve to other MS treatments, and must not currently be enrolled in any other clinical trial of an investigational product, unless according to the study Medical Director it does not conflict with the observational study (e.g., health economic studies). Patients with previous exposure to Plegridy will be evaluated separately from patients who are newly prescribed Plegridy because prevalent Plegridy-users may be more or less likely to experience AEs, may fail to report AEs that occurred before study enrollment, or may have discontinued Plegridy treatment due to an AE. Patients participating in other clinical studies are excluded so as not to unduly confound causality assessments when the safety profile of a concomitant experiment agent has yet to be established and/or the physician is blinded to the patient's treatment assignment.

The decision to enroll a patient in this study must not be made until after the Prescribing Physician and patient decide to begin Plegridy treatment and Plegridy treatment has been prescribed. Patients (or their legally authorized representative) agreeing to participate in the study will read and sign the informed consent and confidentiality statements. Enrollment data will be collected by the Prescribing Physician at the routine clinical visit at which Plegridy is first prescribed. For patients with previous exposure to Plegridy prior to enrollment, data will be collected from the time of first dose of Plegridy through enrollment in this or previous studies (see Section 8.3.1 for details). During enrollment, the Prescribing Physician will also inform female patients of childbearing potential if a pregnancy registry is being conducted independently of this observational study.

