8.2.4.8. Non-initiation of Plegridy and Continued Participation in the Study

Consenting patients who are prescribed Plegridy, but do not take at least one dose of Plegridy after enrollment into the study, will continue to be followed for up to 60 months after enrollment, unless death, withdrawal, or loss to follow-up occurs.

Patients who do not initiate treatment with Plegridy can start Plegridy treatment as part of routine clinical practice at any time.

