8.6.4.2. Methods of Analysis

The incidence and incidence rate of all reported SAEs and AEs will be summarized by Medical Dictionary for Regulatory Activities (MedDRA) system organ class and preferred term. Incidence is defined as the proportion of patients with a given event out of the number of patients in the analysis population. Incidence rate is defined as the number of patients with a given event adjusted for the duration of follow-up for the particular event (e.g., incidence rate per 100,000 per years). Ninety-five percent CIs for incidence and incidence-rate point estimates will be calculated using the binomial distribution and the Poisson distribution, respectively.

Incidence of SAEs and AEs will be stratified by event severity and by relationship to treatment with Plegridy. AEs leading to discontinuation of Plegridy will be summarized separately. Analyses of SAEs and AEs may also be described by characteristics of the sites, Prescribing Physicians, and/or patient subgroups defined by appropriate demographic and/or baseline prognostic factors, and/or concomitant medication exposure (e.g., concomitant MS therapies). Analyses may also be stratified by duration of Plegridy treatment or study duration. Specific subgroup analyses will be described in the SAP.

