8.6.5.4. Secondary Endpoints Analysis

Plegridy prescription and utilization

Duration of Plegridy use and prescribed dosing frequency will be summarized both descriptively and categorically, as appropriate. Primary reasons for discontinuation of Plegridy will be tabulated. Plegridy use will also be described by concomitant medications.

Clinical disease activity (relapse activity and disability progression)

Relapse activity will be assessed by evaluating by relapse-related endpoints. These analyses will include the following parameters:

- ARR: defined as the total number of relapses divided by the number of patient-years on study divided by 12 months.
- Time to first relapse: defined as time (in days) between the date of initiating Plegridy to date of onset of first relapse following Plegridy initiation. Please refer to Section 8.3.6 for the definition of relapse.

CONFIDENTIAL

The information contained herein may not be used, disclosed, or published without the written consent of Biogen MA Inc.

- Proportion of patients with relapse: The proportion of patients with relapse will be described by counts and percent.
- Distribution of the number of relapses: The distribution of the number of relapses will be summarized using mean (SD) and median (minimum and maximum).

Disability progression will be assessed by evaluating disability progression-related endpoints. These analyses will include the following parameters:

- Proportion of patients with sustained progression for at least six months. For the purposes of this study, progression is defined as at least a 1.0 point increase from baseline in EDSS ≥ 1.0 or at least a 1.5 point increase from a baseline EDSS = 0.
- Time to sustained progression for at least six months.

ARR will be analyzed using a negative binomial model, adjusted for appropriate prognostic factors. If the data are under-dispersed or if the negative binomial regression model does not converge, a Poisson regression model with the same covariates will be used instead. Time to sustained progression will be analyzed using Kaplan-Meier estimates.

In addition, Poisson regression model and Cox proportional hazard model might be applied to assess the association between certain demographic variables, baseline disease characteristics, or medical history variables of interest and ARR/time to sustained disability progression, respectively.

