10.2. Monitoring and Recording Events

10.2.1. Adverse Events

The Prescribing Physician should review all AEs experienced by a patient from the time the patient signs the ICF and record the following events in the eCRF:

CONFIDENTIAL

The information contained herein may not be used, disclosed, or published without the written consent of Biogen MA Inc.

- SAEs
- AEs (including laboratory abnormalities) leading to discontinuation of Plegridy treatment
- AEs of special interest (FLS, ISRs)

All other non-serious AEs will not be collected as part of this study. The process for reporting these non-serious AEs should follow spontaneous postmarketing rules as per local regulations.

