10.2.2. Serious Adverse Events

Any SAE experienced by a patient between the time the patient signs the ICF and before study completion or premature study withdrawal, or within 30 days of discontinuation of Plegridy, is to be recorded on an SAE Form, regardless of the event's relationship to Plegridy. It is the responsibility of the Prescribing Physician to report pharmacovigilance information for other MS products per local regulations. For patients who discontinue treatment but continue to participate in the study, any serious events, including malignancies that occur within 30 days after the last dose of Plegridy will be treated as SAEs and reported on an SAE form. For reporting timelines and procedures, see Section [10.2.4](#).

MS relapses will not be automatically reported as an SAE unless the relapse was fatal or, in the opinion of the Prescribing Physician, the relapse was complicated by other SAEs.

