EDSS information (Functional System Scores and Ambulation Scores), based on neurological examination, if consistent with local practice	X	X	X	X
Neurological assessment, if not EDSS	X	X	X	X
MS relapse information, if applicable	X	X	X	X
Use of immunomodulatory, immunosuppressive (including corticosteroids), and anti-neoplastic agents, and other approved MS therapies after discontinuing Plegridy, if applicable		X	X	X
Pregnancy status and nursing status (female patients)	X	X	X	X
PROs ⁴ : EQ-5D-3L, FLS, healthcare resource consumption questionnaire, treatment adherence questionnaire, ⁵ FLS-VAS ⁶	X ⁴	X	X	X
AEs of special interest (FLS, ISR)	X ----->			
AEs [including laboratory abnormalities] leading to treatment discontinuation)	X ----->			
SAEs	X ----->			

CONFIDENTIAL

The information contained herein may not be used, disclosed, or published without the written consent of Biogen MA Inc.

1. Data are to be collected according to local clinical practice, preferably within four weeks (before or after) the time of a clinic visit. Data collection will be inclusive of healthcare visits (e.g., clinic, emergency room, etc.) resulting in a diagnosis of MS relapse that occurs within the three-month (Year 1) or six-month (Year 2 through Year 5) data collection period. MS relapse will be confirmed by the Prescribing Physician (see Section 8.3.6 for the relapse definition). No visits or examinations, laboratory tests or procedures are mandated as part of this study.
2. Baseline is defined as the date of enrollment. Data will be collected from the time of first dose through enrollment for patients who had exposure to Plegridy prior to study enrollment.
3. If a patient withdraws prior to completing the study, all information already collected as part of the study will be retained for the analysis; however, no further efforts will be made to obtain or record additional information regarding the patient.
4. PROs may be completed electronically or on paper at a routine visit if consistent with local regulations. If a patient does not complete his/her PROs during the clinic visit then he/she can complete the PROs electronically via the secure, personalized link within four weeks of his/her routine clinical visit. PROs completed on paper will be entered into the EDC by the site.

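### For newly prescribed patients, cNEDA, ARR, progression and SAE counts open at enrollment, before any Plegridy, while time to first relapse opens at the first dose

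*Protocol*

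**What the plan says.** The footnote to the schedule in Protocol Section 16.1 fixes the reference date: "Baseline is defined as the date of enrollment". Section 8.2.4.1 ties enrollment to consent ("At the time of consent, the patient will be enrolled into the study") and, for new prescriptions, to the prescribing visit: "Enrollment data will be collected by the Prescribing Physician at the routine clinical visit at which Plegridy is first prescribed". No drug is supplied by the study (Section 8.1), and Section 8.2.4.8 leaves the start open: "Patients who do not initiate treatment with Plegridy can start Plegridy treatment as part of routine clinical practice at any time".

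A patient joins the safety and effectiveness analyses by consenting and taking a dose during the study (Sections 8.6.4.1 and 8.6.5.1); effectiveness also requires eligibility. The endpoints are then anchored as follows:

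- **cNEDA (co-primary):** cumulative windows that open at baseline (Section 8.6.5.3).
- **ARR:** all relapses over patient-years on study (Section 8.6.5.4).
- **Progression:** EDSS increase from baseline (Section 8.6.5.4).
- **SAEs (co-primary):** Section 10.2.2 records "Any SAE experienced by a patient between the time the patient signs the ICF and before study completion or premature study withdrawal", and Section 10.2.1 likewise says "The Prescribing Physician should review all AEs experienced by a patient from the time the patient signs the ICF". Section 8.6.4.2 then states that "The incidence and incidence rate of all reported SAEs and AEs will be summarized", with no restriction to events after the first dose.
- **Time to first relapse:** "time (in days) between the date of initiating Plegridy to date of onset of first relapse following Plegridy initiation" (Section 8.6.5.4).

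**The concern.** A naïve patient who consents at the prescribing visit, relapses in week 6 and takes the first dose in week 10 fails Year-1 cNEDA and adds a relapse to the ARR. For time to first relapse, the same event does not exist. A patient who first doses in Year 2 contributes a Year-1 cNEDA result that is wholly pre-treatment.

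The pre-dose interval may be spent on an earlier MS drug or on none, so what it adds is not an effect of Plegridy. The issue sits in the Plegridy-naïve group, which Sections 8.6.3 and 8.6.4.1 analyze separately, and it weighs most on the one-year window. If follow-up for safety rates is also counted from enrollment, pre-dose time enters the denominator for injection site reactions, which cannot occur before an injection.

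The protocol uses treatment start as the reference elsewhere: for concomitant medication (Section 8.2.4.6), baseline ambulation status (Section 8.3.2) and prior MS treatment (Section 8.6.3). The enrollment anchor is therefore not applied consistently.

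**Working it through.** **1. The protocol's own precision figure.** Section 8.6.7 gives n = 1100, dropout up to 20% (880 remaining), expected one-year cNEDA 0.684 and a two-sided 95% CI. Half-width = 1.96 × √(0.684 × 0.316 / n):

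- n = 1100: 0.0275
- n = 880: 0.0307

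This reproduces the stated 0.027 to 0.031. It refers to all patients. The naïve group is smaller and its interval wider; if half the patients were naïve (an assumption), n = 550 and 440 give 0.039 and 0.043.

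**2. Net effect on naïve Year-1 cNEDA.** The protocol states neither the delay nor a pre-dose event rate, so both are assumed.

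- On-drug hazard: h_on = −ln(0.684) = 0.380 per year, assumed constant.
- Pre-dose rate of events that end cNEDA: h_pre = 0.4 to 0.6 per year, assumed constant.
- Delay as a fraction of Year 1: g = weeks/52.

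Counted from first dose, Year-1 cNEDA is exp(−h_on) = 0.684. Counted from enrollment it is exp(−[h_pre × g + h_on × (1 − g)]). The loss is 0.684 × (1 − exp(−(h_pre − h_on) × g)), where h_pre − h_on is 0.0202 or 0.2202.

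| Delay | g | Loss, h_pre = 0.4 | Loss, h_pre = 0.6 |
|---|---|---|---|
| 4 weeks | 0.077 | 0.1 points | 1.1 points |
| 8 weeks | 0.154 | 0.2 points | 2.3 points |
| 12 weeks | 0.231 | 0.3 points | 3.4 points |

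If h_pre = h_on the loss is zero; if an earlier therapy held h_pre below h_on, the sign would reverse.

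**3. Cross-check from the protocol's figures.** Section 6.2.2 reports a 36% lower ARR than placebo with dosing every two weeks. Applying that to the cNEDA hazard (an assumption, since it is a relapse-rate effect) gives h_pre = 0.380/0.64 = 0.593. The losses are then 1.1, 2.2 and 3.3 points for 4, 8 and 12 weeks, near the top of the ranges above.

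**4. Longer windows.** Section 8.6.7 expects 3520 to 3960 person-years, or 3.2 to 3.6 years per patient. A delay of 4 weeks is 0.077/3.6 to 0.077/3.2, or 2.1% to 2.4% of that; 12 weeks is 6.4% to 7.2%. The dilution of ARR and SAE rates over full follow-up is therefore smaller than in Year 1. No SAE rate is given, so the effect on SAE incidence cannot be quantified.

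**The case against.** The strongest reply is that enrollment is a usual baseline for a cohort followed regardless of treatment, that the sentence sits in a data-collection footnote, and that recording events from consent does not attribute them to the drug. Index dates and treatment-emergent rules often sit in the SAP, which is not shown, and Sections 8.6.3 and 8.6.4.1 defer the naïve and population definitions to it. Part of this stands: the SAP may restrict the SAE analysis. But the protocol fixes baseline rather than deferring it, and its endpoint definitions rely on that baseline or on time on study.

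Four stronger readings are tempting, and the document does not support them.

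- **Pre-dose SAEs are presented as caused by Plegridy.** Section 10.3.1 lists occurrence before administration as an example of a not-related event, and Section 8.6.4.2 stratifies by relationship. They stay in the total but are not attributed to the drug.
- **The 68.4% is a benchmark.** Section 8.6.7 uses it only to compute CI width; no comparison with it is planned.
- **Pre-dose deaths are a defect that re-anchoring cures.** Any population that requires a dose excludes them, whichever date is day 0.
- **The bias equals the share of patients who relapse before dosing.** That share, 1 − exp(−rate × weeks/52), is 3–5%, 6–9% and 9–13% for 4, 8 and 12 weeks at 0.4–0.6 relapses per year. It is a gross count. Moving day 0 shifts the 12-month window, and the time added at its end carries its own events.

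It is also fair that, with short delays and no mandated examinations, the last EDSS before the first dose will often be the enrollment EDSS.

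**Conclusion.** The point holds as a matter of text. For Plegridy-naïve patients who later take a dose, pre-dose events would be counted in cNEDA, ARR, EDSS progression and total SAE incidence, and time to first relapse uses a different origin. Never-dosed patients are outside the analyses, and Plegridy-experienced patients are not affected.

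The size cannot be fixed from the document. On the assumptions above, a 4-week delay costs at most about one point of Year-1 cNEDA. At the upper assumed rate, a 12-week delay costs 3.4 points, slightly more than the all-patient half-width of 2.7 to 3.1 points but within the wider interval of the naïve group if that group is half the cohort. The change should be made because it is cheap and removes an inconsistency, not because a large bias has been shown.

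**What to change.** In Sections 8.6.4.2, 8.6.5.3 and 8.6.5.4 and the Section 16.1 footnote:

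1. For Plegridy-naïve patients, define analysis day 0 for cNEDA, ARR, progression and SAE/AE incidence as the first within-study Plegridy dose, with the last EDSS on or before that date as reference.
2. List events between consent and first dose separately as pre-treatment.
3. Keep enrollment as day 0 for Plegridy-experienced patients.
4. Reconcile the time-to-first-relapse origin with these rules, stating it for each group.

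Plegridy start dates are already collected (Section 8.3.3 and the schedule in Section 16.1), so the cost is a few sentences and some programming; data collection is unchanged. The downside is that naïve follow-up shortens by the delay, late starters contribute less than five years, and yearly cut-points no longer fall exactly on the enrollment-based collection schedule.

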16.2. EUROQOL EQ-5D, 3-LEVEL (EQ-5D-3L)

Health Questionnaire (English version for the US)

Health Questionnaire (English version for the US)

By placing a checkmark in one box in each group below, please indicate which statements best describe your own health state today.

Mobility

- I have no problems in walking about
- I have some problems in walking about
- I am confined to bed

Self-Care

- I have no problems with self-care
- I have some problems washing or dressing myself
- I am unable to wash or dress myself

Usual Activities (e.g. work, study, housework, family or leisure activities)

- I have no problems with performing my usual activities
- I have some problems with performing my usual activities
- I am unable to perform my usual activities

Pain/Discomfort

- I have no pain or discomfort
- I have moderate pain or discomfort
- I have extreme pain or discomfort

Anxiety/Depression

- I am not anxious or depressed
- I am moderately anxious or depressed
- I am extremely anxious or depressed

[figure not shown]
CONFIDENTIAL

The information contained herein may not be used, disclosed, or published without the written consent of Biogen MA Inc.

To help people say how good or bad a health state is, we have drawn a scale (rather like a thermometer) on which the best state you can imagine is marked 100 and the worst state you can imagine is marked 0.

We would like you to indicate on this scale how good or bad your own health is today, in your opinion. Please do this by drawing a line from the box below to whichever point on the scale indicates how good or bad your health state is today.

**Your own
health state
today**

CONFIDENTIAL

The information contained herein may not be used, disclosed, or published without the written consent of Biogen MA Inc.

16.3. FLU-LIKE SYMPTOMS (FLS) ASSESSMENT

Select the statement which best describes your MUSCLE ACHES, CHILLS and FATIGUE after your most recent injection.

- absent
- mild, did not interfere with daily activities
- moderate, interfered with daily activities
- severe, bed rest required

If you used any medication to reduce your Flu-Like Symptoms, please select the statement which best describes your MUSCLE ACHES, CHILLS and FATIGUE after taking the medication.

- absent
- mild, did not interfere with daily activities
- moderate, interfered with daily activities
- severe, bed rest required

If you experienced Flu-Like symptoms, did your symptoms last.

- 24 hours or less
- Greater than 24 hours

CONFIDENTIAL

The information contained herein may not be used, disclosed, or published without the written consent of
Biogen MA Inc.

16.4. Healthcare Resource Consumption Questionnaire

PATIENT ID:

QUESTIONNAIRE DATE:

VISIT TIMEPOINT:

Patient Questionnaire – Resource Utilization

A. This questionnaire was filled out by: (mark only one response)

- Patient alone with no assistance
- Patient with assistance
- Family member / Friend / Family caregiver
- Paid caregiver

B. What is your living situation

- Private home, alone or with family or friends, but able to take care of myself
- Private home with family or friend as caregiver
- Private home with home health aide support
- Assisted living

This survey asks how Multiple Sclerosis (MS) affects your use of healthcare services and the impact it has on particular areas of your life. This is not a test. There are no right or wrong answers. If you are unsure how to answer any question, please give the best answer you can.

Please include the healthcare services you have received at any MS center, office or clinic, and hospital, including the facility at which you were recruited for this study.

Questions 1 to 3 refer to the period of time since your last visit before the completing this questionnaire.

1. How many times have you visited these healthcare professionals (HCP) in an 'Outpatient Department' of a clinic or hospital for managing your MS?

HCP	Number of Visits	HCP	Number of Visits
Neurologist – MS Specialist		Physical therapist / Physiotherapist	
Neurologist – not an MS Specialist		Occupational therapist	

CONFIDENTIAL

The information contained herein may not be used, disclosed, or published without the written consent of Biogen MA Inc.

General Practitioner / Primary Care Provider / Internist		Rehabilitation therapist	
Physician assistant		Speech therapist	
Nurse – MS Specialist		Psychiatrist/Psychologist	
Nurse – not an MS specialist		Urologist	
Visiting nurse (visited you)		Gynecologist	
Chiropractor		Counselor	

Other HCP: _____ Number of visits: _____

Other HCP: _____ Number of visits: _____

Other HCP: _____ Number of visits: _____

I did not make any visits: _____

2. Have you been admitted to any of the following facilities due to MS? Yes No
- Nursing home
 - Home or residential hospice or MS centers

3. If you answered ‘Yes’ to question 2, please fill out the following table for details on the admissions. Please fill out each admission on a separate row.

Which facility were you admitted to?	Were you admitted due to relapse?	How many days were you admitted?
 Nursing home  Home/residential hospice or MS centers	 Yes  No	
 Nursing home  Home/residential hospice or MS centers	 Yes  No	
 Nursing home  Home/residential hospice or MS centers	 Yes  No	
 Nursing home  Home/residential hospice or MS centers	 Yes  No	
 Nursing home  Home/residential hospice or MS centers	 Yes  No	

CONFIDENTIAL

The information contained herein may not be used, disclosed, or published without the written consent of Biogen MA Inc.

Caregiver Services

4. Do you have a family caregiver (a family member or friend) who helps you because of problems due to MS?
 - Yes (If yes, please continue to question 5)
 - No (If no, please do not answer the questions below and skip to the next section)

5. Do any of the following apply to your family/friend caregiver?
 - Caregiver works full-time (Employed outside the home) (if yes, please answer questions 6-8)
 - Caregiver works part-time (Employed outside the home) (if yes, please answer questions 6-8)
 - Caregiver works in the home only
 - Caregiver does volunteer work
 - Caregiver is retired
 - None of the above

6. If the caregiver is employed, how many days per week does he/she usually work? _____

7. If the caregiver is employed, in the *past 2 weeks*, how many days did he/she miss work because of helping you because of the problems you experience with MS? _____

8. Has care giving for you caused the caregiver to... (select all that apply)
 - Cut back on his/her hours at work?
 - Leave his/her job?
 - Hire other caregivers by paying out of pocket?
 - Seek government-funded chore services (e.g., home help)?
 - Other, specify _____
 - None of the above

CONFIDENTIAL

The information contained herein may not be used, disclosed, or published without the written consent of
Biogen MA Inc.

